In a number of cases, the situation continues to worsen, with chest pain, respiratory discomfort, and a radiological pattern of viral pneumonia. Signs related to involvement of other organs have been described (neurological, dermatological, etc.).

This clinical picture may be severe enough to justify hospitalization in nearly 20% of symptomatic patients and admission to intensive care in 5% of these cases. These severe forms predominantly affect certain high-risk groups, particularly older and more fragile individuals, who represent the main cause of Covid-19-related deaths.

Clinical presentation and challenges

Initial descriptive studies came from China, but European and American data suggest differences. Incubation lasts about 5 days (range 2–12). Symptoms, when present, develop progressively: headache, muscle pain, fatigue, then fever and respiratory signs 2–3 days later. Some cases worsen with chest pain, dyspnea, and viral pneumonia. Multisystemic manifestations have been reported. Around 20% of symptomatic cases require hospitalization; 5% require ICU admission—mainly affecting elderly and fragile patients.

The main diagnostic test aims to detect viral RNA in nasal secretions or sputum, quantified by RT-PCR. This PCR test, which is rather uncomfortable, appears to have a substantial false-negative rate (~30%).

Screening for minimally symptomatic or asymptomatic forms — which are likely no less contagious — is essential to slow the pandemic and prevent overwhelming the healthcare system. At present, no systematic screening strategy has been implemented in France.

Numerous serological tests detecting IgG and IgM antibodies are emerging. They are much simpler and faster than RT-PCR.

While antibody production (IgM and/or IgG) is known to be detectable from the second week after symptom onset in the general population, recent studies report the appearance of IgM and IgG antibodies as early as the 4th day after onset of clinical signs.

However, the kinetics of IgM/IgG antibody production are poorly characterized in asymptomatic or mildly symptomatic individuals, and even less so in patients with pre-existing conditions (cancer or other causes of immunosuppression).

Finally, high IgG and IgM antibody titers appear to be independently associated with disease severity.

Covid and cancer

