--	---

	
c. Contact with infected individuals at work or at home d. Use of community care
 
Describe the incidence of Covid-19 infections among patients and healthcare personnel.
 
Compare the distribution of contamination risk factors among patients and those of the general population (Constances cohort).
 
Describe adherence to SARS-CoV-2 vaccination among personnel and patients.
 
WP 5 : PSYCHOLOGY OPTIONAL FOR CENTERS
 
Examine the evolution of state anxiety over time and determine whether perceptions of anxiety evolve, indicating a possible adaptation process.
 
Examine associations between post-traumatic growth, trait anxiety, sociodemographic variables, and the evolution of state anxiety over time.
 
Examine the evolution of depression over time and determine whether perceptions of depression evolve, indicating a possible adaptation process.
 
Examine associations between post-traumatic growth, trait anxiety, sociodemographic variables, and the evolution of depression over time.

INCLUSION CRITERIA:	
 1) Age \geq 18 years; 2) Population from a CLCC meeting one of the following three definitions: 
  patients undergoing treatment,  patients in follow-up (having completed their treatment more than one year prior to inclusion),  healthcare personnel; 3) Subjects having had or not had an infection compatible with, or confirmed as, Covid-19; 4) Subjects informed and having signed the informed consent form; 5) Subject affiliated with a social security system.
NON-INCLUSION CRITERIA:	
 1) Refusal to provide consent; 2) Patients unable to give consent or presenting psychiatric history; 3) Inability to comply with medical follow-up for geographical, social, or psychological reasons; 4) Individuals under legal protection (guardianship or curatorship); 5) Individuals deprived of liberty by judicial or administrative decision.
PRIMARY EVALUATION CRITERION:	
Biological data: Serological status (rapid immunochromatographic test) and IgM and IgG titers (enzyme immunoassay, ELISA type), performed at M0, M3, M6, M9, and M12. Collection via questionnaire of results from tests detecting SARS-CoV-2 viral genome (RT-PCR molecular test) performed in community settings
 
Clinical data: Follow-up questionnaire on clinical signs suggestive of Covid-19.

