COMPLETION EVALUATION CRITERION:	
WP 1: SEROLOGY MANDATORY
 
Time to appearance and titers of anti-SARS-CoV-2 IgM and IgG at the different measurement timepoints in each subgroup. Specificity, sensitivity, PPV (Positive Predictive Value), and NPV (Negative Predictive Value) from the different tests, with quantitative serology (ELISA) considered the gold standard.
 
IgG levels at M12.
 
Number of reinfections or viral reactivations (appearance of clinical signs confirmed by RNA tests — RT-PCR positive — and serology) in the subgroup of patients who developed IgG.
 
Anti-SARS-CoV-2 IgG titers according to the occurrence or absence of reinfection during follow-up.

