	
Time to appearance and titers of anti-SARS-CoV-2 antibodies according to FCGR2A and FCGR3A genotypes.
 
IgG-positive results on rapid TROD tests and semi-quantitative ELISA IgG titers in vaccinated individuals.
 
Number of vaccinated individuals in whom anti-Spike protein IgG titration is feasible.
 
Number of vaccinated individuals with positive neutralization test results.
 
WP 2: CLINICAL MANDATORY
 
Number of Covid-19-related deaths, severe infections (requiring oxygen therapy), prolonged symptomatic infections, moderate infections, and asymptomatic infections, relative to all subjects in the population with seropositivity and/or a positive RT-PCR test, as well as duration of the symptomatic phase.
 
Reinfection cases are defined as recurrence of clinical symptoms and/or positive viral PCR and/or positive IgM serology after a symptom-free interval. Frequency is defined as the number of reinfection cases relative to all subjects in the population with seropositivity and/or a positive RT-PCR test.
 
Among subjects in the population with seropositivity and/or a positive RT-PCR test, factors significantly associated with severe forms / mortality among the following:
 
 ○ Ongoing or recent anticancer treatment: 
 - Immunotherapy - Chemotherapy, according to frequency of grade 3/4 neutropenia and/or lymphopenia - Radiotherapy - Surgery ○ Concomitant treatments ○ Comorbidities ○ Cancer (cancer type, stage, etc.) ○ Cancer-related medical history (number of treatment lines, surgical and medical history) ○ Biological markers (CRP, etc.) 
WP 3: ECONOMIC ANALYSIS OPTIONAL FOR CENTERS
 
Type of organizational and practice changes implemented and their frequency according to specialties/services.
 
Total number of patients affected and number of patients per type of change.
 
Positive or negative effects on patient morbidity or mortality.
 
Monetary value of resources mobilized (increased or decreased) depending on observed changes.
 
Number and duration of healthcare personnel sick leave.
 
Benefits of organizational changes for healthcare personnel.
 
Costs of systematic screening of patients and healthcare personnel..
 
WP 4 : PUBLIC HEALTH / EPIDEMIOLOGY OPTIONAL FOR CENTERS
 
Number of SARS-CoV-2 infections among all monitored patients.
 
Prevalence of SARS-CoV-2 infection/immunization during the 3 weeks following the end of lockdown among patients, healthcare personnel working onsite, and healthcare personnel who were confined, by age group, by region (center), and according to comorbidities.
 
Number of SARS-CoV-2 infections among all monitored healthcare personnel.
 
Quarterly incidence rates among patients and healthcare personnel by age group, by region (center), and according to comorbidities.
 
Percentages (qualitative variables) / means or medians (quantitative variables).

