--	--

	
Percentage of personnel and patients refusing vaccination, and distribution according to reasons for refusal.
 
WP 5 : PSYCHOLOGY OPTIONAL FOR CENTERS
 
a. and b. State anxiety score at 3, 6, 9, and 12 months. c. and d. Depression score at 3, 6, 9, and 12 months.
 
Variables assessed at T0 (before screening) State anxiety (STAI-State questionnaire, Spielberger, Gorsuch, Lushene, Vagg & Jacobs, 1983; 20 items) Post-traumatic growth (PTGI, Tedeschi & Calhoun, 1996; 21 items; induction instruction: "since the lockdown"). The PTGI evaluates perceived positive changes such as shifting life priorities, closer relationships with others, developing new interests, etc. Trait anxiety (STAI-Trait questionnaire, Spielberger et al., 1983; 20 items) Sociodemographic variables (related to the Epidemiology WP) Depression (HADS questionnaire, Zigmond & Snaith, 1983; 14 items)
 
At 3, 6, 9, and 12 months (within the week following screening) State anxiety (STAI-State, 20 items) Depression (HADS, 14 items)

--	---

E) DESCRIPTION OF THE STUDY INTERVENTIONS

In this study, screening of patients and healthcare personnel will be performed using two or even three techniques depending on the result:

- **Repeated blood sampling, performed at inclusion (M0), Month 3 (M3), Month 6 (M6), Month 9 (M9), Month 12 (M12), plus on demand in the event of Covid-19 symptoms:**
 - a) Rapid serological test (TDR) — qualitative
 - Performed immediately on site.
 - Technique: immunochromatography strip detecting IgM / IgG.
 - b) Serology by ELISA — quantitative
 - Performed later on frozen samples.
 - c) Genotyping of FCGR2A and FCGR3A genes
 - Performed only at M0.
- **Nasopharyngeal swab (RT-PCR)**
 Detection of viral RNA.

This examination is performed with immediate result exclusively in the event of symptoms, irrespective of the rapid test result, for patients hospitalized in a Covid unit when such a unit exists within the center.

Results of RT-PCR tests performed in community settings (outside the hospital) will be collected via questionnaires.

- **Questionnaires** (Linked to the Work Packages — some are therefore optional)
 - Patients : Q1, Q2, Q3
 - Healthcare personnel : Q1, Q2, Q3, Q4, STAI (ETAT & TRAI), PTGI, HADS

TRIAL SCHEDULE

INCLUSION PERIOD:	12 months
DURATION OF PARTICIPATION PER SUBJECT:	12 months
MINIMUM PARTICIPATION TIME PER PATIENT:	12 months
OVERALL STUDY DURATION:	24 months
START OF THE CLINICAL TRIAL:	June 2020

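### Time to appearance of IgM/IgG is set for every WP 1 subgroup, but three-monthly sampling and undated asymptomatic infections mean it would largely record the visit calendar

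*Protocol*

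**What the plan says.** The relevant statements are in four places in the protocol.

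- **Section D, evaluation criteria for WP 1 (mandatory).** The first criterion is "Time to appearance and titers of anti-SARS-CoV-2 IgM and IgG at the different measurement timepoints in each subgroup". A later one is "Time to appearance and titers of anti-SARS-CoV-2 antibodies according to FCGR2A and FCGR3A genotypes". Neither states the origin from which time is counted.
- **Section E, study interventions.** Blood is taken at inclusion, then at "Month 3 (M3), Month 6 (M6), Month 9 (M9), Month 12 (M12), plus on demand in the event of Covid-19 symptoms". No repeat series after an on-demand draw is described, and the day of that draw relative to onset is not given. The primary evaluation criterion in section D lists serology only at the fixed visits: "performed at M0, M3, M6, M9, and M12".
- **Section C, rationale.** It says that "antibody production (IgM and/or IgG) is known to be detectable from the second week after symptom onset in the general population", and that "recent studies report the appearance of IgM and IgG antibodies as early as the 4th day after onset of clinical signs". It also says that asymptomatic forms are frequent, without a figure.
- **Section E, RT-PCR.** The study's own RT-PCR is confined to symptomatic patients hospitalized in a Covid unit. Community RT-PCR results reach the study through questionnaires.

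The inclusion criteria admit subjects who have already been infected, so some will be positive at M0.

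**The concern.** An event that takes days is to be timed on a grid of about 91 days. For an infection found only at a scheduled visit, the data say that antibodies appeared at some point since the last negative sample. They do not say when the infection began. A time to appearance read off the measurement timepoints then mostly describes how far away the next visit was.

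Symptoms trigger an extra draw, so symptomatic and asymptomatic infections are observed differently. One WP 1 subgroup is symptomatic by definition, while the others may mix both kinds. A subgroup or genotype with more symptomatic cases could appear to seroconvert faster with no difference in biology. Section C names antibody kinetics in asymptomatic subjects and in patients with cancer as poorly known, so readers are likely to take a reported delay at face value.

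**Working it through.** The protocol gives no figure for this criterion, so there is none to reproduce. The check asks what the stated schedule would record.

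**Inputs from the protocol.** Visits are three months apart, D = 365.25/4 = 91.3 days. Appearance runs from day 4 to the second week after onset, taken as delays s of 4 to 14 days. One extra draw is taken if symptoms occur.

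**Assumptions not in the protocol.** Onset is uniform within a visit interval. The biological SD of the delay is 3 days. The on-demand draw falls a mean of 2 to 14 days after onset (SD 2). Symptomatic shares are 50% and 80%. Onset is taken as known for everyone, which favours the protocol. Each scenario was simulated with 400,000 infections.

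**Step 1: scheduled visits only.** The first positive visit comes a uniform 0 to D days after antibodies appear, so the recorded mean is s + D/2.

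- s = 4: 4 + 45.7 = 49.7 days (simulated 49.9)
- s = 10: 10 + 45.7 = 55.7 days (simulated 55.7)
- s = 14: 14 + 45.7 = 59.7 days (simulated 59.6)

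The SD is √(D²/12 + 3²) = √(26.36² + 9) = 26.5 days. The interval alone gives 91.3/√12 = 26.4, so almost none of the spread is biological.

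**Step 2: order of IgM and IgG.** If IgM appears on day 4 and IgG on day 14, a scheduled visit falls between them with probability 10/91.3 = 11%. In the other 89% both are first positive at the same visit.

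**Step 3: effect of the symptomatic share, kinetics identical.** The spurious difference in recorded means is (0.80 − 0.50) × g. Here g is the mean with no on-demand draw minus the mean when every case is symptomatic. For a true delay of 10 days:

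- draw at day 2: g = 55.7 − 55.0 = 0.7, difference 0.2 days
- draw at day 7: g = 55.7 − 46.8 = 8.9, difference about 2.7 days
- draw at day 14: g = 55.7 − 20.2 = 35.5, difference about 10.6 days

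Simulated differences between 50% and 80% symptomatic, in days:

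| True delay | Draw day 2 | Draw day 7 | Draw day 10 | Draw day 14 |
|---|---|---|---|---|
| 4 | 3.5 | 9.9 | – | 10.9 |
| 7 | – | 6.4 | 9.9 | 11.2 |
| 10 | 0.2 | 2.7 | – | 10.6 |
| 14 | 0.1 | 0.3 | – | 6.3 |

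A dash marks a combination that was not run. A further run over draw days 0 to 21 gave a largest value of 11.4 days. Where the difference is near zero, the draw came too early to be positive. Those symptomatic cases then wait for the next scheduled visit too, and the calendar effect of Step 1 applies to them in full.

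**The case against.** **Undated cases cannot bias a mean they do not enter.** Without an onset date no delay from onset exists, so the criterion might be said to cover dated cases already. This has force: Step 3 applies only if asymptomatic infections are given some origin. But the criterion is set for each subgroup without that limit and names no origin. Either the undated cases are out, and the criterion should say so, or a substitute origin is used and the result is driven by the calendar. Dated cases first positive at a scheduled visit still carry the Step 1 error.

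**This belongs in the SAP.** Censoring rules do. An SAP cannot date an undated infection or recover a delay of days from quarterly samples, and the scope of the criterion is fixed in the protocol.

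**Some asymptomatic infections can be dated.** A positive community RT-PCR would do so. The symptom questionnaires, which are in annexes not shown, may record onset dates. Both points stand and are what make the fix workable.

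**Titers are unaffected as measurements.** The same criterion covers titers at each visit, and the schedule supports those.

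Three stronger readings are tempting but unsupported:

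- A reader might compute a spurious difference of 0.30 × 45.7 = 14 days. That needs every on-demand draw to be positive as soon as antibodies appear. The protocol does not time the draw, and a draw at onset would usually precede antibodies. No simulated scenario reached 14 days.
- A reader might infer that WP 1 rests on a formal comparison between treatments. The objective asks for the humoral response in listed subgroups and names no such test. The expected outcomes speak of comparing treated patients with long-term survivors and staff, without reference to time to appearance.
- A reader might infer that non-responders are excluded. The protocol does not say how they are handled.

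**Conclusion.** The point holds for time to appearance, in the subgroup criterion and in the genotype criterion. For infections first seen at a scheduled visit, delays of 4 to 14 days become about 50 to 60 days with an SD of about 26.5 days. This follows from the protocol's own schedule and rationale, given uniform onset between visits.

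The effect of differing symptomatic shares is less certain. It ranges from 0 to about 11 days for an assumed 50% against 80%, and it depends on an unstated draw day and on undated cases being given an origin. It should be cited as a possibility, not as an expected bias.

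This is a secondary criterion. Titers and seropositivity by visit remain usable. The change is still worth making, because the criterion followed as written would give delays that readers could mistake for biology.

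**What to change.** Reword both WP 1 criteria so that time to appearance applies only to subjects with a dated symptom onset or a positive RT-PCR, with that date as the origin. Because the two dates mark different moments, record which one was used.

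Analyse the time as interval-censored between the last negative and the first positive sample. The lower limit is zero where the last negative sample precedes the origin or where none exists, as for subjects already positive at M0. Keep dated subjects who never become positive as right-censored at their last sample.

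For all other infections, drop time to appearance and report the proportion positive and the titer at each visit.

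The cost is a change of wording and a standard analysis, with no new samples. The downside is that fewer subjects contribute. The estimates will also rest mainly on cases with an informative on-demand draw, since the change states the uncertainty correctly but cannot add resolution that the schedule does not have.

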SECONDARY OBJECTIVE:	
WP 1: SEROLOGY MANDATORY
 
Evaluate the humoral response to a Covid-19 infection in the following subgroups:
 
 In patients with cancer who are symptomatic with a probable Covid-19 infection In patients whose treatment has been suspended In patients with treatment currently ongoing: 
 Patients receiving immunotherapy Patients receiving chemotherapy: 
 Patients with neutropenia-inducing chemotherapy Patients with lymphopenia-inducing chemotherapy In healthcare personnel of the CLCCs 
Describe the diagnostic performance of serological tests (IgM rapid test and IgM serological test).
 
Describe long-term IgG persistence and quantification (Month 12) in populations from the CLCCs.
 
Among individuals who developed IgG:
 
 describe the frequency of reinfections in each study population. describe the protective IgG threshold in each study population. 
Evaluate the influence of polymorphisms in low-affinity Fc gamma receptors for IgG (FcγRIIa, FcγRIIIa) on the humoral response.
 
Evaluate the appearance of IgG and their evolution during study follow-up after vaccination.
 
Evaluate the number of individuals presenting antibodies after vaccination.

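### The WP 1 reinfection rule requires a positive RT-PCR that the study performs only in Covid-unit inpatients, so it undercounts reinfections and makes the count depend on access to testing

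*Protocol*

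**What the plan says.** **The rule.** In the protocol's section D, the WP 1 completion criterion counts reinfections or reactivations among those who developed IgG as "appearance of clinical signs confirmed by RNA tests — RT-PCR positive — and serology". All three elements are needed.

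**What it serves.** The WP 1 secondary objective is to "describe the frequency of reinfections in each study population", and also to describe a protective IgG threshold. The criterion that follows the count is "Anti-SARS-CoV-2 IgG titers according to the occurrence or absence of reinfection during follow-up".

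**Where RT-PCR comes from.** Section E limits the study swab to symptomatic cases, "for patients hospitalized in a Covid unit when such a unit exists within the center". No study swab is described for personnel or for patients not hospitalized in such a unit. There is a second source: "Results of RT-PCR tests performed in community settings (outside the hospital) will be collected via questionnaires". The primary evaluation criterion includes these community results as well.

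**What else is collected.** Blood is taken for the rapid test and ELISA at M0, M3, M6, M9 and M12, and on demand when symptoms occur.

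**What the protocol says about the test and the disease.** The rationale (section C) gives a substantial RT-PCR false-negative rate of about 30% and speaks of frequent asymptomatic forms, without a percentage. It also states: "Around 20% of symptomatic cases require hospitalization".

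**The concern.** The rule makes RT-PCR indispensable, yet RT-PCR is the one element that the study does not collect in a standard way. Three kinds of record fail it:

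- an IgG-positive subject without symptoms whose ELISA results show a new infection between two visits;
- a symptomatic outpatient or staff member who gives the on-demand blood sample but has no community RT-PCR;
- a symptomatic subject whose swab is falsely negative while serology points to a new infection.

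The serology that would reveal these episodes is collected but cannot make a case by itself.

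Two WP 1 results are at stake. The first is reinfection frequency by population, which will partly reflect who gets swabbed. The second is the titer comparison behind the protective threshold: the protocol names only occurrence or absence of reinfection, so a missed case, read literally, counts as absence and blurs the contrast.

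**Working it through.** The protocol gives no expected number of reinfections and no precision target for them, so there is no planned figure to reproduce. The check is the share of true reinfections that the rule can count.

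**Inputs**
- Se, RT-PCR sensitivity for one test per episode: 1 − 0.30 = 0.70 (section C).
- h, share of symptomatic cases with a study swab: 0.20 if every hospitalized case is swabbed (section C hospitalization figure, which describes first infections). This is optimistic, since a center need not have a Covid unit. h = 0 for personnel or a center without a unit.
- c, share of the remaining cases with a reported community RT-PCR: not given, shown from 0 to 1.
- a, asymptomatic share of reinfections: not given, shown at 0, 0.2 and 0.4.
- The serology element is taken as always met, which favours the rule.

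**Formula:** share counted = (1 − a) × Se × [h + (1 − h) × c]

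Example with a = 0, h = 0.20, c = 0: 0.70 × 0.20 = 0.14 counted, so 86% missed. With c = 1: 0.70 × 1 = 0.70 counted, so 30% missed.

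| h | a | c = 0 | c = 0.25 | c = 0.50 | c = 0.75 | c = 1 |
|---|---|---|---|---|---|---|
| 0.20 | 0 | 14% | 28% | 42% | 56% | 70% |
| 0.20 | 0.2 | 11% | 22% | 34% | 45% | 56% |
| 0.20 | 0.4 | 8% | 17% | 25% | 34% | 42% |
| 0 | 0 | 0% | 18% | 35% | 53% | 70% |

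**When are more than half missed?** Setting the formula to 0.5 gives c = [0.5 / ((1 − a) × 0.70) − h] / (1 − h).
- a = 0: c below about 64% (h = 0.20) or about 71% (h = 0).
- a = 0.2: c below about 87% (h = 0.20) or about 89% (h = 0).
- a = 0.4: at every c, since at most 0.6 × 0.70 = 42% are counted.

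**Comparability.** Take two populations with the same true rate, the same a and the same c, one with h = 0.20 and one with h = 0. The ratio of counted frequencies is (0.2 + 0.8c) / c: 0.52 / 0.4 = 1.3 at c = 0.4, 0.60 / 0.5 = 1.2 at c = 0.5, and 1.0 at c = 1. Any difference in community testing between populations comes on top and may act in either direction.

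**Repeat swabs.** If each episode were swabbed twice with independent errors, the share of tested cases missed would fall to 0.30 × 0.30 = 9%. The documents plan no such repeat.

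**The case against.** - **Community tests count.** This is correct. A reinfection outside a Covid unit can satisfy the rule. A reader who looks only at the restricted study swab might infer that most reinfections are lost. The documents do not support that: it depends on the community testing share and the asymptomatic share, and neither is given.
- **The size of the distortion between populations is unknown.** This is also correct. A reader might infer a several-fold difference, but Covid-unit access alone gives only about 1.2 to 1.3 at 40 to 50% community testing. What stands is that the counts are not comparable without knowing who was tested.
- **A strict definition protects specificity, above all for a threshold.** This is a fair reason to keep a confirmed tier and to use it as the reinfection group for titers. It does not justify a single strict count as the frequency in populations with unequal access to the test.
- **WP 2 already has a broader definition.** It does, and symptomatic episodes without a positive RT-PCR can count there. But that changes neither the WP 1 count nor the WP 1 titer split. The two WP 2 wordings also disagree: the objective asks for symptoms with a positive PCR and/or IgM, while the criterion accepts any one of the three.
- **Untested episodes may be handled in a SAP.** They may. That missed cases fall into the absence group is a literal reading, not a stated rule. The case definition itself, however, is fixed in the protocol.
- **Serological cases would make the titer analysis circular.** This stands if status is set by an IgG rise and the titers compared include that rise. The fix has to avoid it.

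**Conclusion.** The point holds in this form. The direction is certain: followed as written, the WP 1 rule undercounts reinfections and never counts asymptomatic ones. With the protocol's own false-negative rate and one test per episode, about 30% of symptomatic reinfections are missed under complete testing. The loss grows to about 86% if there is no community testing and the hospitalized 20% are all swabbed.

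The position within that range cannot be read from the documents. The 30% figure is a cautious remark in the rationale and would be lower with repeat swabs; the 20% is borrowed from first infections. The weakness affects secondary WP 1 results, in a mandatory work package, and should be corrected. The argument does not concern the serology on which the main incidence objective also draws.

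**What to change.** 1. **Frequency.** In the WP 1 criterion, report reinfection in each population in two tiers. Confirmed: a new positive RT-PCR, in-center or community, with or without symptoms. Probable: no positive RT-PCR, but serological evidence of a new infection between consecutive samples with no vaccination in between, with or without symptoms. State the serological rule in advance, including the assay's repeat variation, which the protocol does not give.
2. **Testing share.** Beside each frequency, report the share of symptomatic episodes that had an RT-PCR, so that differences in access are visible.
3. **Titers and threshold.** Use the titer from the last sample before the episode. Keep confirmed cases as the reinfection group. Exclude probable episodes and symptomatic but untested episodes from the absence group. As a sensitivity analysis, count probable cases as reinfections, again with pre-episode titers. Do not classify by an IgG rise and then compare titers that contain it.
4. **Wording.** Reconcile the WP 1 rule with the two WP 2 definitions, or state that they measure different things and why.

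The cost is one reworded criterion and further analysis of results already planned; no test or visit is added. The drawback is that probable cases are less specific, and their detection depends on the humoral response, which may differ between treated patients and personnel. The confirmed-only tier shows how much this matters.
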